### **6.3.5 Pregnancy**

If a study participant inadvertently becomes pregnant while on treatment with a pembrolizumab-based combination treatment, the participant will be immediately discontinued from study treatment. The site will contact the participant at least monthly and document the participant's status until the pregnancy has been completed or terminated. The outcome of the pregnancy will be reported to the Sponsor without delay and within 24 hours if the outcome is a serious adverse experience (eg, death, abortion, congenital anomaly, or other disabling or life-threatening complication to the mother or newborn). The study Investigator will make every effort to obtain permission to follow the outcome of the pregnancy and report the condition of the fetus or newborn to the Sponsor. If a male participant impregnates his female partner, the study personnel at the site must be informed immediately and the pregnancy must be reported to the Sponsor and followed as described in Section 9.3.6.

### **6.3.6 Use in Nursing Women**

It is unknown whether pembrolizumab, MK-1308, MK-4280, or lenvatinib is excreted in human milk. In animal studies, lenvatinib has been shown to be excreted in milk. In rat studies, lenvatinib and its metabolites are excreted in rat milk at concentrations higher than in maternal plasma. Because many drugs are excreted in human milk, and because of the potential for serious adverse reactions in the nursing infant, study participants who are breastfeeding are not eligible for enrollment.

### **6.4 Screen Failures**

Screen failures are defined as participants who consent to participate in the clinical study but are not subsequently enrolled in the study. Participants may be rescreened once prior to being considered a screen failure. A minimal set of screen failure information is required to ensure transparent reporting of screen failure participants to meet the Consolidated Standards of Reporting Trials (CONSORT) publishing requirements and to respond to queries from regulatory authorities. Minimal information includes demography, screen failure details, eligibility criteria, and any adverse events or serious adverse events (SAE) meeting reporting requirements as outlined in the entry guidelines.

### **6.5 Participant Replacement Strategy**

A participant who discontinues study treatment or withdraws from the study will not be replaced.

## **7 Treatments**

Study treatment is defined as any investigational treatment(s), marketed product(s), placebo, or medical device(s) intended to be administered to a study participant according to the study protocol.

### **7.1 Treatments Administered**

The combination study treatments to be used in this trial are outlined below in [Table 5](#).

Table 5 Study Interventions

Arm Name	Arm Type	Intervention Name	Intervention Type	Dose Formulation	Unit Dose Strength(s)	Dosage Level(s)	Route of Administration	Regimen/ Treatment Period	Use	IMP or NIMP/ AxMP	Sourcing
Arm 1	Experimental	Pembrolizumab (MK-3475)	Biological/ vaccine	Solution for Infusion	100 mg/vial (25 mg/mL, 4 mL vial)	200 mg	IV infusion	Q3W	Test Product	IMP	Central
Arm 1	Experimental	MK-1308	Biological/ vaccine	Solution for Infusion	50 mg/mL	25 mg	IV infusion	Q6W	Test Product	IMP	Central
Arm 2	Experimental	Pembrolizumab (MK-3475)	Biological/ vaccine	Solution for Infusion	100 mg/vial (25 mg/mL, 4 mL vial)	200 mg	IV infusion	Q3W	Test Product	IMP	Central
Arm 2	Experimental	MK-4280	Biological/ vaccine	Solution for Infusion	25 mg/mL	200 or 800 mg	IV infusion	Q3W	Test Product	IMP	Central
Arm 3	Experimental	Pembrolizumab (MK-3475)	Biological/ vaccine	Solution for Infusion	100 mg/vial (25 mg/mL, 4 mL vial)	200 mg	IV infusion	Q3W	Test Product	IMP	Central
Arm 3	Experimental	Lenvatinib	Drug	Capsule	4 mg, 10 mg	4, 8, 10, 14, or 20 mg	Oral	Once daily	Test Product	IMP	Central

EEA =European Economic Area; IMP=investigational medicinal product; IV=intravenous; NIMP/AxMP=noninvestigational/auxiliary medicinal product; Q3W=every 3 weeks' Q6W=every 6 weeks.
 
The classification of IMP and NIMP/AxMP in this table is based on guidance issued by the European Commission and applies to countries in the EEA. Country differences with respect to the definition/classification of IMP and NIMP/AxMP may exist. In these circumstances, local legislation is followed.
											

All supplies indicated in [Table 5](#) will be provided per the ‘Sourcing’ row depending upon local country operational requirements. Every attempt should be made to source these supplies from a single lot/batch number.

Refer to section 9.1.8 for details regarding administration of the study treatment.

## **7.2 Dose Modification (Escalation/Titration/Other)**

### **7.2.1 Immune-Related Events and Dose Modification (Withhold, Treat, Discontinue)**

The investigator may attribute each toxicity event to pembrolizumab, MK-1308, MK-4280, or lenvatinib alone or to the pembrolizumab-based combination treatment. Study participants may not have any dose reductions of pembrolizumab, MK-1308, or MK-4280 in this study. Interruption of either pembrolizumab, MK-1308, or MK-4280 administration or administration of corticosteroids and/or other supportive care is allowed. If toxicity does not resolve or the criteria for resuming treatment are not met, the participant must be discontinued from the agent. Dose interruptions and reductions of lenvatinib are allowed throughout the study. Holding of 1 agent and not the other agent is appropriate if, in the opinion of the investigator, the toxicity is clearly related to 1 of the study treatments. Appropriate documentation is required regarding the drug to which the investigator is attributing the AE. If, in the opinion of the investigator, the toxicity is related to the combination of 2 agents, then both drugs should be held according to recommended dose modifications.

#### **7.2.1.1 Dose Modification and Toxicity Management for Immune-related AEs Associated with Pembrolizumab Monotherapy, Coformulations or IO Combinations**

AEs associated with pembrolizumab monotherapy, coformulation, or IO combination exposure may represent an immune-related response. These irAEs may occur shortly after the first dose or several months after the last dose of pembrolizumab monotherapy, coformulation, or IO combination treatment and may affect more than one body system simultaneously. Therefore, early recognition and initiation of treatment is critical to reduce complications. Based on existing clinical study data, most irAEs were reversible and could be managed with interruptions of pembrolizumab monotherapy, coformulation, or IO combination administration of corticosteroids and/or other supportive care. For suspected irAEs, ensure adequate evaluation to confirm etiology or exclude other causes. Additional procedures or tests such as bronchoscopy, endoscopy, skin biopsy may be included as part of the evaluation.

#### **Attribution of Toxicity:**

When study interventions are administered in combination, attribution of an adverse event to a single component is likely to be difficult. Therefore, while the investigator may attribute a toxicity event to pembrolizumab monotherapy, coformulations, or IO combinations, pembrolizumab monotherapy, coformulations, or IO combinations must be held according to the criteria in the Dose Modification and Toxicity Management Guidelines for Immune-Related Adverse Events.

In these cases where the toxicity is attributed to pembrolizumab coformulations or IO combinations, re-initiation of pembrolizumab as a monotherapy may be considered after communication with and agreement by the Sponsor.

**Holding Study Interventions:**

When study interventions are administered in combination and if the AE is considered immune-related, pembrolizumab monotherapy, coformulations, or IO combinations should be held according to recommended Dose Modification criteria.

If the toxicity does not resolve or the criteria for resuming treatment are not met, the participant must be discontinued from pembrolizumab monotherapy, coformulations, or IO combinations.

**Restarting Study Interventions:**

Participants may restart pembrolizumab monotherapy, coformulations, or IO combinations as described below:

If the toxicities do resolve and conditions are aligned with what is defined in the Dose Modification and Toxicity Management Guidelines for irAEs, pembrolizumab monotherapy, coformulations, or IO combinations may be restarted at the discretion of the investigator.

Dose Modification and Toxicity Management Guidelines for irAEs associated with pembrolizumab monotherapy, coformulations, or IO combinations are provided in [Table 6](#).

For additional guidance on lenvatinib, see Section 7.2.2.

**Table 6 Dose Modification and Toxicity Management Guidelines for Immune-related Adverse Events Associated with Pembrolizumab Monotherapy, Coformulations or IO Combinations**

General instructions:
 
 
1. Severe and life-threatening irAEs should be treated with IV corticosteroids followed by oral steroids. Other immunosuppressive treatment should begin if the irAEs are not controlled by corticosteroids.
 
2. Pembrolizumab monotherapy, coformulations or IO combinations must be permanently discontinued if the irAE does not resolve or the corticosteroid dose is not <math>\leq 10</math> mg/day within 12 weeks of the last treatment.
 
3. The corticosteroid taper should begin when the irAE is <math>\leq</math> Grade 1 and continue at least 4 weeks.
 
4. If pembrolizumab monotherapy, coformulations or IO combinations have been withheld, treatment may resume after the irAE decreased to <math>\leq</math> Grade 1 after corticosteroid taper.
 
				
irAEs	Toxicity Grade (CTCAEv4.0)	Action With Pembrolizumab Monotherapy, Coformulations or IO Combinations	Corticosteroid and/or Other Therapies	Monitoring and Follow-up
Pneumonitis	Grade 2	Withhold	
 
• Administer corticosteroids (initial dose of 1-2 mg/kg prednisone or equivalent) followed by taper
 
	
 
• Monitor participants for signs and symptoms of pneumonitis
 
• Evaluate participants with suspected pneumonitis with radiographic imaging and initiate corticosteroid treatment
 
• Add prophylactic antibiotics for opportunistic infections
 

	Recurrent Grade 2 or Grade 3 or 4	Permanently discontinue		
Diarrhea / Colitis	Grade 2 or 3	Withhold	
 
• Administer corticosteroids (initial dose of 1-2 mg/kg prednisone or equivalent) followed by taper
 
	
 
• Monitor participants for signs and symptoms of enterocolitis (ie, diarrhea, abdominal pain, blood or mucus in stool with or without fever) and of bowel perforation (ie, peritoneal signs and ileus)
 
• Participants with <math>\geq</math>Grade 2 diarrhea suspecting colitis should consider GI consultation and performing endoscopy to rule out colitis
 
• Participants with diarrhea/colitis should be advised to drink liberal quantities of clear fluids. If sufficient oral fluid intake is not feasible, fluid and electrolytes should be substituted via IV infusion.
 

	Recurrent Grade 3 or Grade 4	Permanently discontinue		

irAEs	Toxicity Grade (CTCAEv4.0)	Action With Pembrolizumab Monotherapy, Coformulations or IO Combinations	Corticosteroid and/or Other Therapies	Monitoring and Follow-up
AST / ALT Elevation or Increased Bilirubin	Grade 2 a	Withhold	
 
Administer corticosteroids (initial dose of 0.5-1 mg/kg prednisone or equivalent) followed by taper
 
	
 
Monitor with liver function tests (consider weekly or more frequently until liver enzyme value returned to baseline or is stable)
 

	Grade 3 b or 4 c	Permanently discontinue	
 
Administer corticosteroids (initial dose of 1-2 mg/kg prednisone or equivalent) followed by taper
 
	
T1DM or Hyperglycemia	New onset T1DM or Grade 3 or 4 hyperglycemia associated with evidence of $\beta$ -cell failure	Withhold d	
 
Initiate insulin replacement therapy for participants with T1DM
 
Administer anti-hyperglycemic in participants with hyperglycemia
 
	
 
Monitor participants for hyperglycemia or other signs and symptoms of diabetes
 

Hypophysitis	Grade 2	Withhold	
 
Administer corticosteroids and initiate hormonal replacements as clinically indicated
 
	
 
Monitor for signs and symptoms of hypophysitis (including hypopituitarism and adrenal insufficiency)
 

	Grade 3 or 4	Withhold or permanently discontinue d		
Hyperthyroidism	Grade 2	Continue	
 
Treat with non-selective beta-blockers (eg, propranolol) or thionamides as appropriate
 
	
 
Monitor for signs and symptoms of thyroid disorders
 

	Grade 3 or 4	Withhold or Permanently discontinue d		

irAEs	Toxicity Grade (CTCAEv4.0)	Action With Pembrolizumab Monotherapy, Coformulations or IO Combinations	Corticosteroid and/or Other Therapies	Monitoring and Follow-up
Hypothyroidism	Grade 2-4	Continue	
 
Initiate thyroid replacement hormones (eg, levothyroxine or liothyronine) per standard of care
 
	
 
Monitor for signs and symptoms of thyroid disorders
 

Nephritis and renal dysfunction	Grade 2	Withhold	
 
Administer corticosteroids (prednisone 1-2 mg/kg or equivalent) followed by taper
 
	
 
Monitor changes of renal function
 

	Grade 3 or 4	Permanently discontinue		
Myocarditis	Grade 1	Withhold	
 
Based on severity of AE administer corticosteroids
 
	
 
Ensure adequate evaluation to confirm etiology and/or exclude other causes
 

	Grade 2, 3 or 4	Permanently discontinue		
Ophthalmologic Uveitis, iritis, episcleritis	Grade 2	Withhold	
 
Administer corticosteroid eye drops to participants who develop uveitis, iritis, or episcleritis
 
Permanently discontinue study drugs for immune-mediated ocular disease that is unresponsive to local immunosuppressive therapy
 
	
 
Monitor for signs and symptoms of ophthalmologic disorders
 

All Other irAEs	Persistent Grade 2	Withhold	
 
Based on severity of AE administer corticosteroids
 
	
 
Ensure adequate evaluation to confirm etiology or exclude other causes
 

	Grade 3	Withhold or discontinue e		
	Recurrent Grade 3 or Grade 4	Permanently discontinue		

irAEs	Toxicity Grade (CTCAEv4.0)	Action With Pembrolizumab Monotherapy, Coformulations or IO Combinations	Corticosteroid and/or Other Therapies	Monitoring and Follow-up

AE(s)=adverse event(s); ALT= alanine aminotransferase; AST=aspartate aminotransferase; CTCAE=Common Terminology Criteria for Adverse Events; DRESS=Drug Rash with Eosinophilia and Systemic Symptom; GI=gastrointestinal; IO=immuno-oncology; ir=immune related; IV=intravenous; SJS=Stevens-Johnson Syndrome; T1DM=type 1 diabetes mellitus; TEN=Toxic Epidermal Necrolysis; ULN=upper limit of normal.
 
Note: Non-irAE will be managed as appropriate, following clinical practice recommendations.
 
a AST/ALT: >3.0 to 5.0 x ULN if baseline normal; >3.0 to 5.0 x baseline, if baseline abnormal; bilirubin:>1.5 to 3.0 x ULN if baseline normal; >1.5 to 3.0 x baseline if baseline abnormal
 
b AST/ALT: >5.0 to 20.0 x ULN, if baseline normal; >5.0 to 20.0 x baseline, if baseline abnormal; bilirubin:>3.0 to 10.0 x ULN if baseline normal; >3.0 to 10.0 x baseline if baseline abnormal
 
c AST/ALT: >20.0 x ULN, if baseline normal; >20.0 x baseline, if baseline abnormal; bilirubin: >10.0 x ULN if baseline normal; >10.0 x baseline if baseline abnormal
 
d The decision to withhold or permanently discontinue pembrolizumab monotherapy, coformulations or IO combinations is at the discretion of the investigator or treating physician. If control achieved or ≤ Grade 2, pembrolizumab monotherapy, coformulations or IO combinations may be resumed.
 
e Events that require discontinuation include, but are not limited to: Guillain-Barre Syndrome, encephalitis, myelitis, DRESS, SJS, TEN and other clinically important irAEs (eg, vasculitis and sclerosing cholangitis).
				

**7.2.1.2 Dose Modification and Toxicity Management of Infusion-reactions Related to Pembrolizumab, MK-1308, and MK-4280**

Pembrolizumab, MK-1308, and MK-4280 may cause severe or life-threatening infusion-reactions including severe hypersensitivity or anaphylaxis. Signs and symptoms usually develop during or shortly after drug infusion and generally resolve completely within 24 hours of completion of infusion. Dose modification and toxicity management guidelines on pembrolizumab, MK-4280, and MK-1308-associated infusion reaction are provided in [Table 7](#).

Table 7 Pembrolizumab, MK-1308, and MK-4280 Infusion Reaction Dose Modification and Treatment Guidelines

NCI CTCAE Grade	Treatment	Premedication at Subsequent Dosing
Grade 1 Mild reaction; infusion interruption not indicated; intervention not indicated	Increase monitoring of vital signs as medically indicated until the participant is deemed medically stable in the opinion of the investigator.	None
Grade 2 Requires therapy or infusion interruption but responds promptly to symptomatic treatment (eg, antihistamines, NSAIDs, narcotics, IV fluids); prophylactic medications indicated for $\leq 24$ hrs	Stop Infusion. Additional appropriate medical therapy may include but is not limited to: IV fluids Antihistamines NSAIDs Acetaminophen Narcotics Increase monitoring of vital signs as medically indicated until the participant is deemed medically stable in the opinion of the investigator. If symptoms resolve within 1 hour of stopping drug infusion, the infusion may be restarted at 50% of the original infusion rate (eg, from 100 mL/hr to 50 mL/hr). Otherwise dosing will be held until symptoms resolve and the participant should be premedicated for the next scheduled dose. Participants who develop Grade 2 toxicity despite adequate premedication should be permanently discontinued from further study treatment.	Participant may be premedicated 1.5 h ( $\pm 30$ minutes) prior to infusion of either pembrolizumab, MK-1308, or MK-4280 with: Diphenhydramine 50 mg PO (or equivalent dose of antihistamine). Acetaminophen 500-1000 mg PO (or equivalent dose of analgesic).
Grades 3 or 4 Grade 3: Prolonged (ie, not rapidly responsive to symptomatic medication and/or brief interruption of infusion); recurrence of symptoms following initial improvement; hospitalization indicated for other clinical sequelae (eg, renal impairment, pulmonary infiltrates) Grade 4: Life-threatening; pressor or ventilatory support indicated	Stop Infusion. Additional appropriate medical therapy may include but is not limited to: Epinephrine** IV fluids Antihistamines NSAIDs Acetaminophen Narcotics Oxygen Pressors Corticosteroids Increase monitoring of vital signs as medically indicated until the participant is deemed medically stable in the opinion of the investigator. Hospitalization may be indicated. **In cases of anaphylaxis, epinephrine should be used immediately. Participant is permanently discontinued from further study treatment.	No subsequent dosing
Appropriate resuscitation equipment should be available at the bedside and a physician readily available during the period of drug administration. For further information, please refer to the Common Terminology Criteria for Adverse Events v4.0 (CTCAE) at http://ctep.cancer.gov		

### **7.2.1.3 Other Allowed Dose Interruption for Pembrolizumab, MK-1308, MK-4280 and Lenvatinib**

Pembrolizumab, MK-1308, MK-4280, and lenvatinib may be interrupted for situations other than treatment-related AEs, such as medical/surgical events and/or unforeseen circumstances not related to study treatment. However, intervention is to be restarted within 3 weeks (21 days) of the originally scheduled dose and within 42 days of the previously administered dose, unless otherwise discussed with the Sponsor. The reason for interruption should be documented in the participant's study record.

### **7.2.2 Dose Modifications for Lenvatinib**

Lenvatinib dose reduction and interruption for participants who experience lenvatinib-pembrolizumab combination therapy-related toxicity will be in accordance with the dose modification guidelines described in [Table 8](#). An interruption of study treatment for more than 28 days will require Sponsor's approval before treatment can be resumed.

Adverse events will be graded using NCI CTCAE Version 4.0. Investigators will decide the probability of the event being related to one or both drugs as to whether dose modification of one or both drugs is required.

The starting dose of lenvatinib is 20 mg/day. Dose reductions of lenvatinib occur in succession based on the previous dose level (14, 10, and 8 mg/day). Any dose reduction below 8 mg/day must be discussed with the Sponsor. Once the study drug dose has been reduced, it may not be increased at a later date, unless the dose has been mistakenly decreased; in this situation, Sponsor's approval is required to increase the dose.

Refer to the subsections below for management of hypertension (Section 7.2.2.1), proteinuria (Section 7.2.2.2), diarrhea (Section 7.2.2.3), hepatotoxicity (Section 7.2.2.4), thromboembolic events (Section 7.2.2.5), posterior reversible encephalopathy syndrome/reversible posterior leukoencephalopathy syndrome (PRES/RPLS; Section 7.2.2.6), hypocalcemia (Section 7.2.2.7), hemorrhage (Section 7.2.2.8), gastrointestinal perforation (7.2.2.9), and osteonecrosis of the jaw (7.2.2.10) as appropriate, before consulting the dose modification table ([Table 8](#)).

**Table 8 Adverse Events Requiring Dose Modification of Lenvatinib**

Adverse Event	NCI CTCAE Grade	Action	Dose Adjustment/ Resume Lenvatinib
Hypertension	Grade 3 a	Hold	Resume at reduced dose when hypertension resolves to Grade 0, 1, or 2
	Grade 4	Discontinue	Do not restart treatment
Cardiac dysfunction	Grade 3	Hold	Resume at reduced dose when cardiac dysfunction resolves to Grade 0, 1, or baseline
	Grade 4	Discontinue	Do not restart
Arterial thrombotic event	Any grade	Discontinue	Do not restart
Hepatotoxicity	Grade 3	Hold OR discontinue	Consider resuming at a reduced dose if resolves to Grade 0 to 1 or baseline
	Grade 4	Discontinue	Do not restart
Hepatic failure	Grade 3 or 4	Discontinue	Do not restart
Proteinuria	≥2g/24 hours	Hold	Resume at reduced dose when proteinuria resolves to <2 g/24 hours
	Grade 4	Discontinue	Do not restart
Nephrotic syndrome	N/A	Discontinue	Do not restart
Nausea, vomiting, or diarrhea b	Grade 3	Hold	Resume at reduced dose when nausea, vomiting, diarrhea resolves to Grade 0, 1, or baseline
Vomiting and diarrhea b	Grade 4	Discontinue	Do not restart
Renal failure or impairment	Grade 3	Hold OR discontinue	Consider resuming at a reduced dose if resolves to Grade 0-1 or baseline
	Grade 4	Discontinue	Do not restart
GI perforation	Any grade	Discontinue	Do not restart
Fistula	Grade 3 or 4	Discontinue	Do not restart
QTc prolongation	>500 ms	Hold	Resume at reduced dose when QTc prolongation resolves to <480 ms or baseline
RPLS	Grade 1, 2 or 3	Hold or discontinue	Upon resolution, resume at a reduced dose or discontinue depending on the severity and persistence of neurologic symptoms
	Grade 4	Discontinue	Do not restart
Hemorrhage	Grade 3	Hold	Resume at reduced dose when haemorrhage resolves to Grade 0 or 1
	Grade 4	Discontinue	Do not restart
Other intolerable Grade 2 c,d,e or Grade 3 adverse reactions f,g - first occurrence	Grade 2 or 3	Interrupt lenvatinib until resolved to Grade 0-1, or tolerable Grade 2	Reduce lenvatinib dose to 14 mg once a day e
Other intolerable Grade 2 c,d,e or Grade 3 adverse reactions f,g - Second occurrence (same toxicity or new toxicity)	Grade 2 or 3	Interrupt lenvatinib until resolved to Grade 0-1, or tolerable Grade 2	Reduce lenvatinib dose to 10 mg once a day e

Adverse Event	NCI CTCAE Grade	Action	Dose Adjustment/ Resume Lenvatinib
Other intolerable Grade 2 c,d,e or Grade 3 adverse reactions f,g - Third occurrence (same toxicity or new toxicity)	Grade 2 or 3	Interrupt lenvatinib until resolved to Grade 0-1, or tolerable Grade 2	Reduce lenvatinib dose to 8 mg orally once a day e
Other intolerable Grade 2 c,d,e or Grade 3 adverse reactions f,g - Fourth occurrence (same toxicity or new toxicity)	Grade 2 or 3	Interrupt lenvatinib	Discuss with Sponsor
Grade 4 h	Grade 4	Discontinue	Discuss with Sponsor
CTCAE = common terminology criteria for adverse events; GI = gastrointestinal; N/A = not applicable; NCI = National Cancer Institute; RPLS=reversible posterior leukoencephalopathy syndrome. a. Grade 3 despite optimal anti-hypertensive therapy b. Initiate prompt medical management for nausea, vomiting, or diarrhea. Permanently discontinue for Grade 4 vomiting and diarrhea despite medical management. c. Initiate optimal medical management for nausea, vomiting, hypertension, hypothyroidism, and/or diarrhea prior to any lenvatinib interruption or dose reduction. d. Applicable only to Grade 2 toxicities judged by the participant and/or physician to be intolerable. e. Obese participants (BMI $\geq 30$ ) with weight loss do not need to return to their baseline weight or within 10% of their baseline weight (ie, Grade 1 weight loss). These participants may restart study intervention at a lower dose once their weight remains stable for at least 1 week and they reach at least a BMI of 25. The new stable weight should be used as the new baseline for further dose reductions. f. For asymptomatic laboratory abnormalities, such as Grade $\geq 3$ elevations of amylase and lipase that are not considered clinically relevant by the investigator, continuation of treatment should be discussed with Sponsor. g. For Grade 3 thromboembolic event, permanently discontinue lenvatinib/matching placebo. See Section 7.2.2.5 h. Excluding laboratory abnormalities judged to be non-life-threatening, in which case manage as Grade 3 Note: For grading see National Cancer Institute Common Toxicity Criteria for Adverse Events, v 4.0. Collect all CTCAE grades of AEs, decreasing and increasing grade. Note: An interruption of study treatment for more than 28 days will require Sponsor approval before treatment can be resumed.			

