- If systolic BP  $\geq 160$  mmHg or diastolic BP  $\geq 100$  mmHg recurs on the first dose reduction despite optimal management of hypertension with antihypertensive medications (either by dose increase or the addition of a different class of antihypertensive), then lenvatinib administration should be interrupted and restarted at an additional dose reduction only when systolic BP  $\leq 150$  mmHg and diastolic BP  $\leq 95$  mmHg and the participant has been on a stable dose of antihypertensive medication for at least 48 hours.
- If systolic BP  $\geq 160$  mmHg or diastolic BP  $\geq 100$  mmHg recurs on the second dose reduction despite optimal management of hypertension with antihypertensive medications (either by dose increase or the addition of a different class of antihypertensive), then lenvatinib administration should be interrupted and restarted at a third dose reduction dose only when systolic BP  $\leq 150$  mmHg and diastolic BP  $\leq 95$  mmHg and the participant has been on a stable dose of antihypertensive medication for at least 48 hours.
- Additional dose reduction should be discussed with the sponsor.

The following guidelines should be followed for the management of Grade 4 hypertension (life threatening consequences):

1. Institute appropriate medical management
2. Discontinue study drug.

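### Table 8 fixes the lenvatinib dose by occurrence number without saying whether earlier named-event reductions count, so read literally it conflicts with the step-down rule in Section 7.2.2

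*Combined protocol and SAP*

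**What the plan says.** Section 7.2.2 sets out a ladder. "The starting dose of lenvatinib is 20 mg/day", and then "Dose reductions of lenvatinib occur in succession based on the previous dose level (14, 10, and 8 mg/day"). Below the last level, "Any dose reduction below 8 mg/day must be discussed with the Sponsor". The ladder runs one way: "Once the study drug dose has been reduced, it may not be increased at a later date, unless the dose has been mistakenly decreased", and that exception needs the Sponsor's approval. The same section also makes Table 8 the operative guide for lenvatinib reductions and interruptions.

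Table 8 has two kinds of row.

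- **Named-event rows** (hypertension, cardiac dysfunction, proteinuria, nausea/vomiting/diarrhea, QTc prolongation, hemorrhage and others). Where treatment may resume, these ask for a reduced dose and give no mg figure, so the step is relative to the current dose.
- **Rows for other intolerable Grade 2 or Grade 3 reactions.** These give a fixed dose by occurrence number. The first says "Reduce lenvatinib dose to 14 mg once a day", the second gives 10 mg, the third 8 mg, and the fourth sends the case to the Sponsor. From the second row on, a parenthesis says that the toxicity may be the same one or a new one.

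Section 7.2.2.1 allows successive reductions for hypertension alone. If raised blood pressure recurs on the first reduction despite optimal management, "then lenvatinib administration should be interrupted and restarted at an additional dose reduction only when systolic BP" and diastolic pressure are back within stated limits. A third reduction is also provided for. A participant can therefore be at 14, 10 or 8 mg before any reaction that falls under the other-reaction rows.

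**The concern.** One text moves down from where the participant is. The other names an absolute dose that depends on how many reactions have been counted. They give the same answer only if the count matches the number of reductions already made, and Table 8 does not say that named-event reductions enter the count.

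The sequence needed to expose this is an ordinary one. Grade 3 diarrhea is a named row. Footnote c, attached to the intolerable Grade 2 entry of the other-reaction rows, also mentions diarrhea, along with nausea, vomiting, hypertension and hypothyroidism. A participant could be reduced once for Grade 3 diarrhea and later return with an intolerable Grade 2 reaction that a site files as a first occurrence.

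Two sites could then give different doses to the same participant after a second intolerable toxicity, each able to cite the protocol. Section 10.11 reports deviations from protocol-directed administration, but here the protocol can be read as directing two different actions. Section 10.12 summarises exposure as duration in cycles, so a difference in mg would not show there.

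**Working it through.** **Inputs**

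- Ladder in Section 7.2.2: 20, 14, 10, 8 mg/day, one step from the previous level; anything lower goes to the Sponsor.
- Table 8, other-reaction rows: first 14 mg, second 10 mg, third 8 mg, fourth to the Sponsor.
- Named-event rows: one step down each. Section 7.2.2.1 says one dose level for hypertension. The other named rows say only that the dose is reduced, and one level is assumed for them too.

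**Step 1. Reproduce the table's own sequence.** With no named-event reduction, three successive other reactions give 20 → 14 → 10 → 8 under both texts. They agree, so the table is consistent with the ladder for a participant starting from 20 mg.

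**Step 2. Put named-event reductions first, then a first other reaction, and read the occurrence number literally.** The difference is the first-occurrence dose minus the current dose.

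| Named-event reductions so far | Current dose | Table 8, first occurrence | Difference | Section 7.2.2 |
|---|---|---|---|---|
| 0 | 20 mg | 14 mg | 14 − 20 = −6 | 14 mg |
| 1 | 14 mg | 14 mg | 14 − 14 = 0 | 10 mg |
| 2 | 10 mg | 14 mg | 14 − 10 = +4 | 8 mg |
| 3 | 8 mg | 14 mg | 14 − 8 = +6 | Sponsor |

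With one earlier reduction, the row produces no change where the ladder produces a step. With two or three, the row asks for a reduction to a figure above the current dose, which is not a reduction.

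**Step 3. Vary the order.** Other, named, other: 20 → 14 → 10, and the second-occurrence row then gives 10 mg (10 − 10 = 0), while the ladder gives 8 mg. Named, other, other: the literal table gives 20 → 14 → 14 → 10, while the ladder gives 20 → 14 → 10 → 8.

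**Step 4. Try a cumulative counter in which every dose-reducing toxicity is an occurrence.** One named reduction makes the next reaction the second occurrence: 10 mg, ladder 10 mg. Two make it the third: 8 mg, ladder 8 mg. Three make it the fourth: Sponsor under both. The conflict disappears.

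**Step 5. Ask whether the documents state that counter.** They do not. The parenthesis about the same or a new toxicity sits inside rows headed as other reactions, so it can mean any toxicity of that kind, or any toxicity at all. Footnote c blurs the boundary, because nausea, vomiting, hypertension and diarrhea also have named rows, but it concerns medical management before a dose change and says nothing about counting. No sentence says that the mg figures assume a participant still at 20 mg, or which text prevails.

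**The case against.** The strongest reply is that the surrounding text already points to one sensible reading. The three doses in the other-reaction rows are the ladder of Section 7.2.2 in the same order, so the rows can be taken as that ladder written out from a 20 mg start. The parenthesis about the same or a new toxicity can be read as a cumulative counter, and Step 4 shows that this removes every discrepancy, including at the bottom of the ladder. On that view the problem is one unstated counting rule, and the two rules can be reconciled.

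That reply is fair about what may have been intended. It does not settle what is written. Section 7.2.2 sends sites to Table 8, and Table 8 gives an absolute dose keyed to a count that it does not define for participants already reduced under a named row.

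The reply does defeat a stronger reading that a tempted reader might infer: that Table 8 orders a dose increase. It does not. The cell tells the site to reduce, and Section 7.2.2 forbids a later increase unless the dose was lowered by mistake. At 10 or 8 mg the row is unworkable; it is not an instruction to go up. That case also needs at least two earlier reductions. The likelier practical problem is the milder one, a participant left at 14 mg.

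**Conclusion.** The point holds as an internal inconsistency in the dosing text. Read literally, the other-reaction rows of Table 8 give no reduction to a participant already at 14 mg, where Section 7.2.2 steps down. They give a figure 4 or 6 mg/day above the current dose to a participant already at 10 or 8 mg, which cannot be carried out as a reduction. This rests on counting only reactions of the other kind as occurrences and on one dose level per named-event reduction. If named-event reductions count, the texts agree.

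The number of participants affected cannot be derived. The documents give no rate of named-event reductions and no rate of later intolerable reactions, so any count would rest on unsourced assumptions.

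A reader might also infer that trial results are distorted. The documents do not show that. Sample size and power are unaffected, and planned exposure is summarised in cycles. An effect on adverse events or on discontinuations due to them, both secondary endpoints, is possible but cannot be sized. The case for acting is participant safety and consistent conduct across sites.

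**What to change.** The sponsor's clinical team should reconcile the other-reaction rows of Table 8 with Section 7.2.2 so that both lead to the same action for a participant already reduced under a named row. The text should leave no doubt about how such a reduction bears on the occurrence number, including for the events in footnote c that also have named rows. Sites should be told of the clarification. The choice of dose and counting rule belongs to the clinical team; none is proposed here.

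The cost is a wording change at the next amendment and a memo to sites. No participants, visits or procedures are added.
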